7.2 Subject Disposition and Data Sets Analyzed

Patient disposition will be listed and summarized by treatment group and overall and will include the number and percentage of patients:

- screened;
- entered placebo lead-in period;
- screened and not randomized;
- randomized (i.e. entered the titration period);
- randomized and not treated with double-blind treatment;
- treated with double-blind treatment;
- entered the maintenance period;
- entered the taper period;

COVANCE INC. CONFIDENTIAL

Document Date: 9 July 2018

Page 18 of 39
ST-AD-008 version 04

Downloaded by PPD on 10/12/2022

Statistical Analysis Plan

Sponsor Name: Insys Development Company, Inc.

Sponsor Protocol ID: INS011-16-085

Covance Study ID: 000000163564

- continued to the long-term safety study;
- included in each study population (Safety, ITT, PP, DEXA, PK).

In addition, the number and percentage of patients who complete the study and who discontinue early, including a breakdown of the primary reasons for discontinuation from the study will be presented.

A summary of patient randomization by site will also be provided by treatment group and overall for the ITT population. Inclusion/exclusion criteria not met will be listed for all screened patients.

In addition, a summary table and listing will be produced for discrepancies between the stratification factors in the database and IWRS. This will be produced for the ITT population.

A listing of study drug kit numbers and assignments will be produced.

7.3 Protocol Deviations

All important protocol deviations leading to exclusion from the PP population (see Section 5.3.1) will be summarized by treatment group for the ITT population. The deviations will be identified before data are unblinded.

All protocol deviations will be listed.

7.4 Demographics and Other Baseline Characteristics

Demographic and baseline characteristics will be listed and summarized by treatment group and overall for the ITT population. Standard descriptive statistics will be presented for:

- age (years) [calculated as (screening visit date – date of birth)/365.25 and reported as whole years];
- gender (Male, Female);
- ethnicity (Hispanic or Latino, Not Hispanic or Latino, Unknown);
- race (White, Black or African American, Asian, American Indian or Alaska Native, Native Hawaiian or other Pacific Islander, Other);
- weight (kg) at Screening visit;
- body mass index (kg/m^2) (derived on eCRF);
- randomization strata of growth hormone treatment (Yes, No).

No formal tests of statistical significance will be performed on the demographic and baseline data.

Statistical Analysis Plan

Sponsor Name: Insys Development Company, Inc.

Sponsor Protocol ID: INS011-16-085

Covance Study ID: 000000163564

Other baseline measurements, such as vital signs and ECG, will be summarized by treatment group with the post-baseline measurements.

7.4.1 Patient Global Impression of Severity (PGI-S)

Patient Global Impression of Severity (PGI-S) is assessed at Baseline and is a single item questionnaire where patients are asked to rate the severity of their condition. The response to this assessment ranges from 1: "Normal" to 7: "Extremely ill (I am more sick/ill than I have ever been)". PGI-S response will be summarized by treatment group using standard descriptive statistics. In addition, the number and percentage of patients selecting each response will be summarized.

7.4.2 Medical or Surgical History

Medical or surgical history will be coded using the Medical Dictionary for Regulatory Activities (MedDRA) [Version 21.0 (or a later version if updated during the study)]. All medical or surgical history will be listed, and the number and percentage of patients with any medical or surgical history will be summarized for the ITT population by system organ class (SOC) and preferred term (PT) for each treatment group and overall.

7.4.3 Previous and Concomitant Medications

Medications received prior to or concomitantly with treatment will be coded by Covance using the WHODrug Dictionary [Version March 2018 (or a later version if updated during the study)] Anatomical Therapeutic Chemical (ATC) Classification codes.

Prior medications and concomitant medications are defined as follows:

Prior medications are those taken prior to the first dose date of double-blind IMP treatment.

Concomitant medications are those with a start date on or after the first dose date of double-blind IMP treatment, or those with a start date before the first dose date of double-blind IMP treatment and a stop date on or after the first dose date of double blind treatment or ongoing at the end of the study.

If a medication cannot be classified as "prior" or "concomitant" after applying imputation rules for missing/incomplete dates, it will be classified as concomitant.

Prior medications and concomitant medications will be listed together and summarized separately for the ITT population.

The number and percentage of patients using each medication will be displayed together with the number and percentage of patients using at least one medication within each therapeutic class (ATC-Level 2), chemical subgroup (ATC-Level 4), and generic term.

COVANCE INC. CONFIDENTIAL

Document Date: 9 July 2018

Page 20 of 39
ST-AD-008 version 04

Downloaded by PPD on 10/12/2022

Statistical Analysis Plan

Sponsor Name: Insys Development Company, Inc.
Sponsor Protocol ID: INS011-16-085

Covance Study ID: 000000163564

7.5 Measurements of Treatment Compliance

Percentage compliance is calculated based on the study drug administration page as follows:

$$100 \times \frac{\# \text{ doses taken}}{\text{Expected } \# \text{ doses (based on visit days)}}$$

where # doses taken = # of the "yes" responses to "Was AM dose taken?" and "Was PM dose taken?"

Percentage compliance will be summarized descriptively by treatment group for the Safety population.

The following percentage compliance categories will also be presented:

- <90.0%
- ≥90.0% and ≤110.0%
- >110.0%

In addition, summary statistics of the weights of bottles dispensed and returned, as well as the volume administered, will be presented by treatment group for the Safety population.

All study drug administration and drug accountability data will be listed in full.

7.6 Efficacy

All statistical inference will be based on a comparison of the placebo and all CBD treatment groups. Descriptive statistics for efficacy endpoints will be based on all treatment groups, i.e. placebo, CBD (30 mg/kg/day), CBD (40 mg/kg/day), all CBD and total.

7.6.1 Primary Efficacy Analysis

The primary endpoint, change in total HQ-CT score from Baseline through Study Completion/Early Withdrawal, will be assessed using MMRM.

The MMRM model will include change in total HQ-CT score at each scheduled visit, fixed factors for treatment group, time (study week), randomization strata of growth hormone treatment (yes, no), a treatment-by-time interaction term, and baseline total HQ-CT as a covariate. A contrast will be specified for the primary analysis time point of Study Completion/Early Withdrawal.

All patients in the ITT population with non-missing total baseline HQ-CT score and at least one non-missing post-baseline HQ-CT score will be included in the analysis model. The MMRM will use observed data only, no imputations of missing data will be performed. Stratification factors as used in the IWRS randomization will be

Statistical Analysis Plan

Sponsor Name: Insys Development Company, Inc.
Sponsor Protocol ID: INS011-16-085

Covance Study ID: 000000163564

included. An unstructured covariance matrix will be used to model the residuals over time within each patient. However, in the event that the model does not converge, the following matrices will be used in order until the model converges: Toeplitz, first-order autoregressive and compound symmetry. The least squares (LS) means and their associated 95% confidence intervals (CIs) and p-values will be presented for each treatment group, as well as the LS mean difference, its 95% CI and the comparison p-value.

Graphical presentations of total HQ-CT scores by treatment and visit will be used to examine trends over time, displaying the LS means together with their associated 95% CIs.

In addition, total HQ-CT scores and changes from baseline will be summarized by treatment group and visit using standard descriptive statistics.

This analysis will be repeated for all patients in the per protocol population.

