6.1.2. Hyperphagia Questionnaire-Clinical Trial (HQ-CT)

The HQ-CT will be completed at each Visit (Screening, Placebo Lead-In, Baseline, Week 1, Week 3, Week 5, Week 7, Week 9, Week 11, and Study Completion/Early Withdrawal (Week 13). The questionnaire assesses food-related problem behaviors and consists of three factors: Hyperphagic Drive (internal consistency 0.76), Hyperphagic Behavior (internal consistency 0.80) and Hyperphagic Severity (internal consistency 0.60). It is a 13-item parent completed questionnaire (Fehnel et al., 2015).

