8.6.3.1. Primary Efficacy Analysis

The primary outcome variable for the study is the change in total score of the HQ-CT from Baseline through Study Completion/Early Withdrawal. The primary efficacy endpoint will be tested using a 2-sided type I error rate of 0.05.

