2.3 Sample Size and Power

A total of 30 patients per treatment group will provide at least 85% power with an alpha of 0.05, to detect a difference in the change in HQ-CT from Baseline to Week 13 of 5 points with a standard deviation of 6. Assuming a 20% drop out rate, approximately 66 patients (33 patients per arm) will be randomized to achieve 60 (30 patients per arm) completers.

3. Efficacy and Safety Endpoints

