7.6.4.1 Change in Total Body Weight

Change from Baseline to Study Completion/Early Withdrawal in body weight will be analyzed using the MMRM method described for the primary efficacy endpoint. The MMRM model will include change in total body weight at each scheduled visit, fixed factors for treatment group, time (study week), randomization strata of growth hormone treatment (yes, no), a treatment-by-time interaction term, and baseline total body weight as a covariate.

LS means and the LS mean difference between all CBD and placebo will be presented together with the relevant 95% CIs and p-values. In addition, LS means and the 95% CIs will be plotted by treatment group and visit.

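### The primary MMRM fits one baseline slope for all seven post-baseline visits; if the correlation with baseline decays, the Week 13 contrast loses some precision that one extra model term would recover

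*SAP*

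**What the plan says.** SAP 7.6.1 models the change in total HQ-CT at each scheduled visit. The fixed part contains treatment, study week, growth hormone stratum, "a treatment-by-time interaction term, and baseline total HQ-CT as a covariate". No baseline-by-time term is listed. On the covariance the SAP states: "An unstructured covariance matrix will be used to model the residuals over time within each patient". Toeplitz, first-order autoregressive and compound symmetry are fallbacks if the model does not converge. For inference, "A contrast will be specified for the primary analysis time point of Study Completion/Early Withdrawal".

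Protocol 6.1.2 gives the HQ-CT schedule as screening, lead-in, "Baseline, Week 1, Week 3, Week 5, Week 7, Week 9, Week 11, and Study Completion/Early Withdrawal (Week 13"). Seven post-baseline visits therefore enter the model. Protocol 8.6.3.1 states: "The primary efficacy endpoint will be tested using a 2-sided type I error rate of 0.05".

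SAP 2.3 states: "A total of 30 patients per treatment group will provide at least 85% power with an alpha of 0.05". The planning values are a "difference in the change in HQ-CT from Baseline to Week 13 of 5 points with a standard deviation of 6". The SD is for the change score. Neither document gives a baseline SD, a correlation of baseline with any later score, or a correlation between post-baseline visits.

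SAP 7.6.4.1 uses the same form for body weight: "a treatment-by-time interaction term, and baseline total body weight as a covariate". The only single-time-point ANCOVA in the SAP is in the optional jump-to-reference analysis (SAP 7.6.2).

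**The concern.** The model lets the treatment effect and the residual covariance differ freely from visit to visit, yet holds the baseline slope fixed. That is right for Week 13 only if baseline predicts Week 13 as well as it predicts Week 1. For many rating scales one would expect the correlation with baseline to weaken with time. The slope for the change score then grows more negative over the visits, and a pooled slope falls short of what Week 13 needs. Part of any chance baseline imbalance, and part of the variance that baseline could explain, stays in the primary contrast.

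Precision is what is at stake. The trial is small, and the primary result gates all ten secondary tests (SAP 7.6.3).

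**Working it through.** **Step 1: the plan's own figure.** Inputs from SAP 2.3: 30 per arm, difference 5, SD 6, two-sided alpha 0.05.

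- SE = 6 × √(2/30) = 1.549, and 5/1.549 = 3.227.
- Normal approximation: Φ(3.227 − 1.960) = Φ(1.267) = 89.8%.
- Noncentral t with 58 df: 88.8%.

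The claim of at least 85% holds.

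**Step 2: formula for the loss.** Let b be the vector of visit-specific slopes of the raw score on baseline, and C the covariance of the seven post-baseline scores given baseline. With complete data and unstructured covariance:

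- common slope: b_c = (1′C⁻¹b) / (1′C⁻¹1)
- Week 13 variance inflation = Var(baseline) × (b_13 − b_c)² / C_13,13

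Modelling change instead of the raw score subtracts 1 from every slope and leaves the inflation unchanged.

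**Step 3: numbers.** The correlations are assumptions. SDs are set equal to 1 at all visits, so b_13 is the Week 13 correlation ρ and C_13,13 = 1 − ρ². In the linear rows the correlation between any two visits falls linearly with their separation, from its 1-week to its 13-week value.

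| Assumed correlation | b_c | b_13 | C_13,13 | Inflation |
|---|---|---|---|---|
| Constant 0.6 | 0.600 | 0.6 | 0.64 | 0% |
| Linear 0.7 to 0.5 | 0.632 | 0.5 | 0.75 | 2.3% |
| Linear 0.8 to 0.6 | 0.745 | 0.6 | 0.64 | 3.3% |
| Linear 0.7 to 0.4 | 0.605 | 0.4 | 0.84 | 5.0% |
| Linear 0.8 to 0.5 | 0.726 | 0.5 | 0.75 | 6.8% |
| Linear 0.8 to 0.4 | 0.708 | 0.4 | 0.84 | 11.3% |
| AR(1), Week 13 correlation 0.8 | 0.980 | 0.8 | 0.36 | 9.0% |
| AR(1), Week 13 correlation 0.5 | 0.918 | 0.5 | 0.75 | 23.3% |
| AR(1), Week 13 correlation 0.3 | 0.833 | 0.3 | 0.91 | 31.3% |

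Example, 0.8 to 0.5: (0.726 − 0.5)² / 0.75 = 0.0511/0.75 = 6.8%.

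In every decaying row b_c exceeds b_13, so the change score is under-adjusted. A random intercept plus AR(1) plus measurement noise gave 0.3% to 11%. The result also depends on the correlations among follow-up visits. If baseline correlation falls from 0.7 to 0.5 but all follow-up visits share one correlation, the loss is 2.6% when that correlation is 0.5 and 5.9% when it is 0.8.

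**Step 4: simulation.** With 30 per arm, complete data and 6,000 runs per structure, the variance of the common-slope contrast divided by that of the visit-specific contrast was:

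- 0.993 (constant 0.6)
- 1.018 (0.7 to 0.5) and 1.009 (0.8 to 0.6)
- 1.045 (0.7 to 0.4), 1.055 (0.8 to 0.5) and 1.101 (0.8 to 0.4)
- 1.215 (AR(1), Week 13 correlation 0.5)

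Bias was at most 0.008 SD in absolute value, and the common-slope rejection rate under the null was 4.9% to 5.5%.

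**Step 5: effect on the stated power.** SAP 2.3 gives SD 6 for the change score, which allows nothing for baseline adjustment. The common-slope variance is C_13,13 × (1 + inflation), and the unadjusted change-score variance is 2(1 − ρ). For 0.8 to 0.4 these are 0.84 × 1.113 = 0.935 and 1.2. For AR(1) with Week 13 correlation 0.5 they are 0.75 × 1.233 = 0.925 and 1.0. In every row of the table the SAP model is more precise than the unadjusted comparison on which the sample size rests.

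If SD 6 were instead read as the residual SD after full adjustment, 5% inflation would give 87.2% power and 12% would give 85.1% (noncentral t). At 20% it would be 82.6%.

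**The case against.** The strongest objection is that this is an efficiency refinement of unknown size to a valid, pre-specified analysis. That stands. With constant correlation the simpler model is marginally better, with mild decay the gain is slight, and no document figure tells us which case applies.

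Four stronger readings are tempting, and the documents do not support them.

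- **A definite loss, such as 5-12%.** A figure like that needs particular assumed correlations. Protocol 6.1.2 reports internal consistency for three HQ-CT factors, which says nothing about correlation over time.
- **The protocol's ANCOVA would be more precise than the SAP's MMRM.** Protocol 8.6.3 itself provides for a repeated measures analysis where there are multiple values, so the MMRM is no departure. It also uses the earlier visits of patients who drop out. A large-sample calculation with 20% evenly spread dropout put the ratio of completers' ANCOVA variance to common-slope MMRM variance at 1.05 with constant correlation, 1.03 with mild decay and close to 1.00 for 0.7 to 0.4 and 0.8 to 0.5. Only under steeper decay, 0.85 to 0.44, did ANCOVA win clearly (0.94).
- **The planned power fails.** Step 5 shows otherwise at 30 per arm. It is true that 66 × 0.80 = 52.8 leaves fewer than 60 completers, but that is a separate matter of the dropout arithmetic and does not come from the baseline slope.
- **The same gain applies to every model in SAP 7.6.4.** Nothing was computed for those endpoints. TFEQ-R18, PROMIS and PGI-C have only three post-baseline visits. PGI-C is not a change score and is adjusted for PGI-S, so the argument does not carry over to it directly.

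**Conclusion.** The point holds as a conditional, low-cost improvement. As written, SAP 7.6.1 applies one baseline slope to seven visits. If the baseline correlation decays, the Week 13 contrast is under-adjusted. The variance cost is 0% (constant), about 2-3% (0.7 to 0.5 or 0.8 to 0.6), about 5-11% (0.7 to 0.4 up to 0.8 to 0.4), and more than 20% under AR(1)-type decay to a Week 13 correlation of 0.5 or below.

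These bands assume equal SDs, complete data, unstructured covariance and, for the middle two, linear decay across all pairs of visits. They treat the Study Completion/Early Withdrawal time point as Week 13. The fallback covariance structures were not examined.

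A reader might infer bias or an inflated false-positive rate. Neither follows: randomization keeps the contrast unbiased, and simulated type I error stayed near 5%.

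**What to change.** Before unblinding, add a baseline total HQ-CT by visit interaction to the primary MMRM in SAP 7.6.1. Keep treatment-by-visit, the growth hormone stratum and the unstructured covariance as they are. Alternatively, state in the SAP why a common slope is expected to hold through Week 13.

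The cost is one model term, or 7 − 1 = 6 extra fixed-effect parameters, with no new data or visits. If the correlation is constant, the price is roughly 1% in variance (simulated ratio 0.993).

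Extending the term to the change-score MMRMs in SAP 7.6.4, including body weight in 7.6.4.1, is optional and for consistency only. PGI-C would need its own justification.

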2.2 Overall Study Design

This study is a double-blind, randomized, placebo-controlled, Phase 2 clinical trial in patients aged 8 to 17 years inclusive, with a genetically confirmed diagnosis of PWS.

Approximately 66 patients will be randomized in a 1:1 ratio to receive either:

- Cannabidiol Oral Solution (40 mg/kg/day) divided into twice daily doses with standard meal
- Matching placebo, divided into twice daily doses with standard meal

Randomization will be stratified according to use of growth hormone (Yes, No).

Patients will participate in the study for approximately 19 weeks. The study will consist of the following 6 periods:

- Screening Period (2 weeks)
- Placebo Lead-in Period (2 weeks)
- Titration Period (1 week)
- Maintenance Period (12 weeks)
- Taper Period (1 week)
- Follow-up Period (1 week)

Eligible patients will be assigned to a 2-week single-blind placebo lead-in period after which they will be randomly assigned to receive double-blind treatment with either Cannabidiol Oral Solution (40 mg/kg/day) or matching placebo (a 1-week Titration Period followed by a 12-week Maintenance Period). During the Titration Period Cannabidiol Oral Solution will be titrated as follows: Days 1-3: 20 mg/kg/day, Days 4-6: 30 mg/kg/day, Day 7: 40 mg/kg/day.

During the Maintenance Period, patients may have their dose of blinded study medication adjusted down to 30 mg/kg/day at the discretion of the investigator or qualified designee based on the patient's tolerability.

After completion of the study, patients will be offered an opportunity to enroll into an open-label, long-term safety study. Patients who do not elect to enroll in the long-term safety study will be titrated off study drug over 7 days and a final safety follow-up phone call will be placed 2 weeks after study completion for patients who do not elect to continue in the long-term safety study.

[figure not shown]
Statistical Analysis Plan

Sponsor Name: Insys Development Company, Inc.
Sponsor Protocol ID: INS011-16-085

Covance Study ID: 000000163564

The study design is depicted in [Figure 1](#).

Figure 1: Study Design Schematic

All screening, efficacy and safety evaluations will be performed according to the schedule of assessments summarized in [Appendix A](#).

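### If the unstructured model fails, every fallback covariance in SAP 7.6.1 assumes equal variance at all visits, so the Week 13 test can exceed 5% type I error if the spread of change grows over time (low priority)

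*SAP*

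**What the plan says.** SAP 7.6.1 analyses change in HQ-CT total score with a repeated-measures model and tests a contrast at Study Completion. The covariance rule starts with: "An unstructured covariance matrix will be used to model the residuals over time within each patient". If that model does not converge, "the following matrices will be used in order until the model converges: Toeplitz, first-order autoregressive and compound symmetry". The section names no heterogeneous-variance version, no empirical (sandwich) standard error, no degrees-of-freedom method and no retry with other starting values.

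The same rule reaches most of the secondary tests. Body weight (7.6.4.1) "will be analyzed using the MMRM method described for the primary efficacy endpoint", and 7.6.4.3 to 7.6.4.6 refer to the same method for PGI-C, the three TFEQ-R18 subscales and the four PROMIS scores. That is nine of the ten secondary tests. The exception is responder rate, which uses Fisher's exact test.

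On error control, protocol 8.6.3.1 states: "The primary efficacy endpoint will be tested using a 2-sided type I error rate of 0.05". SAP 7.6.3 claims family-wise control at 0.05, with the primary test as the gate and Hochberg over the ten secondary hypotheses.

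**The concern.** Toeplitz, first-order autoregressive and compound symmetry, as listed, each pool a single variance over all visits. The tested contrast sits at the last visit. If patients' changes from baseline spread out as the study goes on, the pooled variance understates the Week 13 variance. The model-based standard error is then too small, the confidence interval too narrow and the p-value too low.

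Growing spread is plausible. The first post-baseline visit is Day 7, at the end of titration, when changes have had little time to diverge. It is more plausible for weight in growing children than for HQ-CT, but the documents establish it for neither.

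For the three-visit endpoints (Weeks 3, 9 and 13) there is a second, smaller mismatch. The gaps are 6 and 4 weeks, and Toeplitz and AR(1) indexed by visit order treat them as equal.

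At stake is the validity of the primary p-value in the one situation where the preferred model has already failed. A change of structure after unblinding would be post hoc.

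**Working it through.** **Inputs from the documents.** Two-sided alpha 0.05 (protocol 8.6.3.1). From SAP 2.3, 30 completers per arm and a difference "of 5 points with a standard deviation of 6". 33 randomized per arm, 1:1 (SAP 2.2 and 2.3). HQ-CT and weight are measured at Weeks 1, 3, 5, 7, 9, 11 and 13 (protocol 6.1.1, 6.1.2). TFEQ-R18, PROMIS and PGI-C are measured post-baseline at Weeks 3, 9 and 13 (protocol 6.1.3-6.1.5, 6.1.8). No SD at another visit, no weight SD and no between-visit correlation is given, so all variance profiles below are assumptions.

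**The plan's own figure.** SE = 6 × √(2/30) = 1.549 and 5/1.549 = 3.227. Power = Φ(3.227 − 1.960) = 89.8% (88.8% with the noncentral t), which agrees with the stated minimum of 85%.

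**Covariance parameters.** Unstructured needs k(k+1)/2 parameters. Seven visits: 7 × 8/2 = 28 (HQ-CT, weight). Three visits: 3 × 4/2 = 6 (the other eight repeated-measures tests).

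**Closed form.** With complete data, a common-variance model bases the Week 13 SE on the average variance over visits. This is exact for compound symmetry and approximate for the other two. Let R = mean variance over visits / Week 13 variance. Then type I error = 2(1 − Φ(1.96√R)). Only the ratio matters, so it makes no difference that the SD of 6 is not adjusted for baseline.

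HQ-CT, SD changing linearly over the seven visits:

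| SD, Week 1 to Week 13 | Mean variance | R | Type I error |
|---|---|---|---|
| 6 to 6 | 36.00 | 1.000 | 5.0% |
| 5 to 6 | 30.36 | 0.843 | 7.2% |
| 4 to 6 | 25.44 | 0.707 | 9.9% |
| 3 to 6 | 21.25 | 0.590 | 13.2% |
| 7 to 6 | 42.36 | 1.177 | 3.3% |

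Weight:
- Variance proportional to time: R = 7/13 = 0.538, type I error 15.0%.
- Variance proportional to time squared: R = 65/169 = 0.385, type I error 22.4%.
- Random walk plus visit noise with SD half the Week 13 spread: R = 0.692, type I error 10.3%.

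**Simulation.** REML fits of the SAP model, 33 per arm, 20% completely random dropout, t reference with 62 df, 1000 trials per scenario, Monte Carlo error about 0.7-1.4 points.

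| Scenario | Toeplitz | AR(1) | CS | Unstructured |
|---|---|---|---|---|
| HQ-CT, constant SD | 4.9% | 4.7% | 6.0% | 5.2% |
| HQ-CT, SD 5 to 6 | 7.5% | 7.3% | 8.2% | 5.6% |
| HQ-CT, SD 4 to 6 | 11.2% | 11.0% | 11.7% | 5.7% |
| Weight, random walk | 15.7% | 15.5% | 16.9% | 6.5% |
| Weight, random slope | 15.6% | 20.7% | 24.8% | 6.1% |

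For HQ-CT with SD 4 to 6, the mean fallback SE was 1.30-1.33 against an actual SD of the estimate of 1.66. The unstructured fit converged in all 5 × 1000 = 5000 trials.

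**Does the remedy work?** Adding an uncorrected sandwich SE to the three fallbacks brought type I error to 5.8-6.5% (HQ-CT) and 6.3-7.2% (weight). Heterogeneous structures were checked only by fitting them to assumed population covariances (large sample, complete data, model-based errors):
- HQ-CT, SD 4 to 6, AR(1) correlation 0.8: heterogeneous Toeplitz and AR(1) gave 5.0%, heterogeneous compound symmetry 3.9%.
- Weight, random walk or random slope with moderate noise: heterogeneous structures alone still gave about 5-13%.

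So neither change is enough on its own. Small-sample-corrected sandwich errors and Kenward-Roger were not simulated.

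**The case against.** The strongest reply is that the rule may never operate. It applies only if the unstructured fit fails, and that did not happen in 5000 simulated trials of this size. If, for illustration, failure had a 2% chance and the conditional error were 10%, the overall rate would be 0.98 × 5% + 0.02 × 10% = 5.1%. This largely stands and is why the priority is low. The simulation used an EM algorithm on clean data, so it suggests that failure is uncommon without proving it for the planned software. The SAP itself thought the contingency worth a rule.

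The second reply is that nothing in the documents shows growing variance. This also stands. A reader might infer from the list of structures alone that the Week 13 standard error must be too small, or attach one inflated rate to each endpoint. The documents do not support that: with a constant SD the test holds its level, and with a falling SD it is conservative.

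Two further inferences fail:
- The burden of 28 parameters does not extend to every test. The eight three-visit tests need 6, so non-convergence there is much less likely and the unequal-gap issue is minor.
- The weight rate is not the trial's error rate. It is a per-test figure for an endpoint reached only after the primary succeeds and then tested within Hochberg.

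Against the remedy, it can fairly be said that sandwich errors do not remove bias in the estimate when the covariance is misspecified and dropout is at random rather than completely at random.

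**Conclusion.** The point holds conditionally. Given non-convergence, and given variance of change that grows over visits, all three listed fallbacks understate the Week 13 standard error and the per-test type I error exceeds 5%. For HQ-CT the range across constant to strongly growing spread is about 5-13%: about 7-8% if the SD rises from 5 to 6, and about 10-12% if it rises from 4 to 6. For weight it is about 10-25% under assumed growth. If the SD does not grow, there is no inflation. Because the primary test is the gate in SAP 7.6.3, an inflated primary test would also undermine the family-wise claim. The weight figure alone would not translate directly into a family-wise rate.

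Both conditions are unverified and the first looks uncommon. This is a low-priority improvement to a contingency rule.

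**What to change.** Replace the fallback sentence in SAP 7.6.1 with this sequence:
1. Unstructured, with Kenward-Roger degrees of freedom.
2. If it does not converge, unstructured again with alternative starting values.
3. Then heterogeneous Toeplitz, heterogeneous AR(1) and heterogeneous compound symmetry, in that order, with small-sample-corrected empirical (sandwich) standard errors whenever one of these is used.

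Apply the same rule to the three-visit endpoints, and allow no homogeneous or equal-spacing structure with model-based errors there. A standard spatial structure is not a remedy, because it handles the unequal gaps but still assumes a common variance.

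The cost is a few lines of SAP text before unblinding, with no change to conduct, data or sample size. Sandwich errors are somewhat more variable at about 66 patients, hence the correction. They do not repair bias from a wrong covariance under dropout at random, which is why the heterogeneous structures are needed as well.
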